3.4.2 Visit Window

A windowing convention will be used to determine the assignment of immunogenicity laboratory assessments to a nominal study visit for analyses summarized by visit. Samples collected outside of the analysis visit windows defined in Table 3 will be excluded from by-visit analyses.

Table 3 Analysis Visit Windows for Immunogenicity Data

Visit Description	Visit Number	CSP Visit Window		Analysis Visit Window	
		Days Relative to Visit	Study Day	Days Relative to Visit	Study Day
Baseline	1	≤ 1	1	≤ 1	1

Visit Description	Visit Number	CSP Visit Window		Analysis Visit Window	
		Days Relative to Visit	Study Day	Days Relative to Visit	Study Day
Day 29 post-vaccination	3	+3	29-32	±5	24-34
Day 181 post-vaccination	4	±14	167-195	Same as CSP Visit Window	

In the event of multiple assessments within a single analysis visit window, then the following rules will be applied:

- If there are two or more observations within the same visit window, then the non-missing observation closest to the scheduled visit will be used in the analysis;
- If two observations are equidistant from the scheduled visit, then the non-missing observation with the earlier collection date will be used in the analysis;
- If two observations are collected on the same day, then the non-missing observation with the earlier collection time will be included in the analysis. If the collection time is not available, the scheduled assessment will be favored over the unscheduled assessment.

If a visit window does not contain any observations, then the data will remain missing.

3.4.3 Handling of Unscheduled Visits

Not applicable.

3.4.4 Multiplicity/Multiple Comparisons

There are no planned multiplicity adjustments for this descriptive study.

3.4.5 Handling of Protocol Deviations in Study Analysis

Only important protocol deviations (IPDs) will be extracted from the Clinical Trial Management System (CTMS) for inclusion in reporting datasets and PD summaries. The study team will identify and document a final list of IPDs prior to database lock. The process for identification and assessment of protocol deviations, including a full list of IPDs, is detailed in a separate protocol deviation management plan developed by Syneos Health. Participants who are identified as having experienced an IPD may be excluded from the analysis sets or may have their data following the IPD excluded from the analyses.

4 STATISTICAL ANALYSIS

This section provides information on definitions, derivation, and analysis/data presentation per domain.

4.1 Study Population

The domain study population covers participant disposition, analysis sets, protocol deviations, demographics, baseline characteristics medical history, prior and concomitant medication, eDiary compliance, and duration of follow-up.

4.1.1 Participant Disposition and Completion Status

4.1.1.1 Definitions and Derivations

Disposition and completion status can be obtained directly from the eCRF.

4.1.1.2 Presentation

Disposition will be summarized by vaccination group and overall.

The disposition summary will include:

- Participants screened
- Participants not randomized (including reasons not randomized)
- Participants randomized
- Participants randomized, not vaccinated (including reasons not vaccinated)
- Participants who received study intervention
- Participants ongoing in study at data cut-off date (primary analysis)
- Participants who completed the study
- Participants withdrawn from the study (including reasons for early withdrawal)

Only counts will be presented for the number of participants screened, screen failures, participants randomized, and randomized, not vaccinated. For all other categories the denominator for percentages will be the number of participants who received study vaccine.

4.1.2 Analysis Sets

4.1.2.1 Definitions and Derivations

Analysis sets are defined in Section 3.3.

4.1.2.2 Presentation

The number of participants included in each analysis set (by actual vaccination group) will be summarized. The number of participants excluded from each defined analysis set along with the reason for exclusion will also be summarized. A participant may be excluded from an analysis set for more than one reason. They will be counted once for the number of participants excluded from each set and once for each reason for exclusion.

The number and percentage of participants included in each analysis set by site will also be presented, with the denominator for calculation of percentages being the number of participants in the analysis set. No summaries will be presented by vaccination group using the Screened set.

4.1.3 Protocol Deviations

4.1.3.1 Definitions and Derivations

Protocol deviations are defined as instances in which participants or investigational site study personnel fail to adhere to the protocol requirements. Important protocol deviations are a subset of protocol deviations that may significantly impact the completeness, accuracy, and/or reliability of the study data or that may significantly affect a participant's rights, safety, or well-being. Deviations are collected in the CTMS. A detailed list of possible IPDs and the process for identifying and assessing them by the clinical study team will be outlined in the PDNC management plan developed by Syneos Health. The protocol deviation categories will be reviewed by the medical and statistical team members before the CDL and classified as non-important or important per the PDNC plan.

4.1.3.2 Presentation

All IPDs will be extracted from the CTMS for inclusion in reporting datasets and PD summaries, while non-IPDs will be available in the CTMS system but will be excluded from reporting in the CSR.

Important PDs will be summarized for participants in the safety set. The number and percentage of participants with at least one IPD, as well as the number and percentage by category will be presented by vaccination group. The total number of participants will be presented for each protocol deviation category. The same participant may have more than one IPD within a category and will be counted once in each category. The denominator for percentages will be the number of participants in the safety analysis set.

Deviations in the following categories will be reviewed on a regular basis (as outlined in the PDNC plan) for consideration as important for the evaluation and implementation of the study:

- Concomitant Medication
- Inclusion or exclusion criteria

- Informed consent
- Investigational product
- Met Withdrawal Criteria but was not Withdrawn
- Patient Privacy
- Randomization
- SAE not reported or reported late
- Study Procedure
- Visit Schedule

4.1.4 Demographics

4.1.4.1 Definitions and Derivations

Demographic information will be directly obtained from the eCRF. Age and year of birth will be collected in the eCRF and integrated into the IRT system.. The denominator for calculation of percentages will be the number of participants in the analysis set. Participants will be excluded from the summary (eg, means) of an individual parameter if data are missing.

4.1.4.2 Presentation

Demography data will be summarized for the Safety and Immunogenicity analysis sets. Demographics will be summarized descriptively for the entire study population, by study group, and by age subgroup category. Demographic parameters will include:

- Age (years) at consent
- Gender at birth
- Race
 - American Indian or Alaska Native
 - Asian
 - Black or African American
 - Native Hawaiian or Other Pacific Islander
 - White or Caucasian
 - Japanese or Japanese descent
 - Other
- Ethnicity
 - Hispanic or Latino
 - Not Hispanic or Latino
 - Not reported/specify

4.1.5 Baseline Characteristics

4.1.5.1 Definitions and Derivations

Height and weight will be taken directly from the eCRF. The BMI will be calculated as weight in kilograms divided by height in meters squared.

4.1.5.2 Presentation

Baseline characteristics will be presented along with demography and will be summarized for the Safety analysis sets. Participants will be excluded from the summary (eg, means) of an individual parameter if data are missing. Baseline characteristics will include:

- Height (m)
- Weight (kg)
- BMI (kg/m²)

4.1.6 Disease Characteristics

This study includes normal healthy participants and therefore summaries of baseline disease characteristics are not applicable.

4.1.7 Medical History and Concomitant Disease

4.1.7.1 Definitions and Derivations

Medical history can be obtained directly from the eCRF.

4.1.7.2 Presentation

The number and percentage of participants will be summarized for the safety set by MedDRA system organ class and preferred term. Medical history will be classified according to the MedDRA (initial version 27.0). Participants with multiple occurrences will be counted once per system organ class and preferred term regardless of the number of medical history occurrences. The denominator for calculation of percentages will be the number of participants in the safety set.

4.1.8 Concomitant Medications

4.1.8.1 Definitions and Derivations

A concomitant medication, which will be documented in the eCRF, is any medication that is taken on or after signed informed consent to treat an SAE or AESI, or if they are prohibited according to the CSP. Medications used to treat medical history conditions or other adverse events are otherwise recorded only in the source document.

4.1.8.2 Presentation

The number and percentage of participants who take concomitant medications will be summarized for the safety set by ATC classification and generic drug name. Concomitant medications will be classified according to the WHO-Drug Dictionary (initial version WHODrug Global B3 Mar 2024). Participants will be counted once per ATC classification and generic drug name regardless of the frequency of medication usage. The denominator for calculation of percentages will be the number of participants in the analysis set.

4.1.9 Study Drug Compliance

A single dose of study vaccine will be administered by study site staff and therefore study drug compliance issues are not foreseen for this study. Summaries of study drug compliance are not planned, however the number and percentage of participants who receive study vaccination will be included in the disposition summary described in Section 4.1.1.

4.1.10 Duration of Follow-up

4.1.10.1 Definitions and Derivations

Duration of follow-up will be calculated for the study periods, Day 1 to Day 29 and Day 1 to Day 181, as the number of days from vaccination to the end of the follow-up period or study discontinuation, whichever is earlier [eg minimum (Study Day 29 visit date, discontinuation date) – vaccination date + 1].

4.1.10.2 Presentation

The number of participants, mean, standard deviation, median, minimum, and maximum duration of follow-up (in days) will be summarized for participants in the Safety analysis set, for each study period.

4.1.11 eDiary Compliance

4.1.11.1 Definitions and Derivations

The eDiary compliance rate will be measured as the number and percentage of days where the eDiary was completed, for participants in the safety analysis set. Participants will be categorized as either 100% compliant (8 days completed), partially compliant (6-7 days completed), poorly compliant (1-5 days completed), or non-compliant (0 days completed).

4.1.11.2 Presentation

The number of participants, mean, standard deviation, minimum and maximum eDiary compliance rate will be summarized for participants in the safety analysis set. Number and percentage of participants by compliance category will also be presented. The denominator for the calculation of percentages will be the number of participants in the safety analysis set.

4.2 Endpoint Analyses

The following table section covers details related to the primary and exploratory endpoint analyses.

Table 4. Primary and exploratory estimands

Statistical category	Endpoint	Population	Intercurrent event strategy	Population level summary (analysis)	Details in section
Objective 1: To characterize the nAb responses to RSV A in serum following vaccination with IVX-A12 or licensed RSV vaccine					
Primary Analysis of the Immunogenicity Endpoint	RSV A (GFP MN RSV A Assay, [REDACTED] nAb concentrations at Day 29)	Immunogenicity analysis set	Participant follow-up will be censored at the date of intercurrent event (IPD that may impact immune response, infection with RSV/hMPV, early withdrawal, death)	Model-adjusted GMCs by vaccination group 
 Unadjusted GMCs/GMFRs from baseline by vaccination group Proportion of participants with seroresponse (GMFR ≥ 4 from baseline) by vaccination group. 	4.2.1.5 4.2.1.7
Objective 2: To assess the safety of single IM vaccination with IVX-A12 or licensed RSV vaccine					
Primary Analysis of the Safety Endpoint	Immediate unsolicited AEs within 30 minutes of dosing	Safety analysis set	N/A	Incidence by vaccination group (descriptive)	4.6
	Injection site and systemic solicited ARs through 7 days post-vaccination (Day 1 to Day 8)		N/A	Incidence by vaccination group (descriptive)	4.6
	Unsolicited AEs through 28 days post-vaccination (Day 1 to Day 29)		N/A	Incidence by vaccination group (descriptive)	4.6
	SAEs, MAAEs, and AESIs through 6 months post-vaccination (Day 1 to Day 181)		N/A	Incidence by vaccination group (descriptive)	4.6
Objective 3: To characterize the durability of the nAb responses to RSV A in serum following vaccination with IVX-A12 or licensed RSV vaccine					
Exploratory	RSV A nAb concentrations through Day 181	Immunogenicity analysis set	Participant follow-up will be censored at the date of intercurrent event (IPD)	
 Model-adjusted GMCs by vaccination group and visit 	4.2.3

Statistical category	Endpoint	Population	Intercurrent event strategy	Population level summary (analysis)	Details in section
			that may impact immune response, infection with RSV/hMPV, early withdrawal, death)	
 Unadjusted GMCs/GMFRs from baseline by vaccination group and visit Seroresponse rate by vaccination group and visit 	
Objective 4: To compare the nAb responses to RSV in serum following vaccination with IVX-A12 or licensed RSV vaccine					
Exploratory	RSV A nAb concentrations through Day 181	Immunogenicity analysis set	Participant follow-up will be censored at the date of intercurrent event (IPD that may impact immune response, infection with RSV/hMPV, early withdrawal, death)	
 Model-adjusted GMCs by vaccination group and visit Model-adjusted GMC ratios by visit Unadjusted GMCs /GMFRs from baseline by vaccination group and visit Seroresponse rate by vaccination group by post-baseline visit Difference in seroresponse rate by post-baseline visit 	4.2.3
Exploratory	RSV B nAb concentrations through Day 181				
Objective 5: To compare the nAb responses to hMPV in serum following vaccination with IVX-A12 or licensed RSV vaccine					
Exploratory	hMPV A nAb titers through Day 181	Immunogenicity analysis set	Participant follow-up will be censored at the date of intercurrent event (IPD that may impact immune response, infection with RSV/hMPV, early withdrawal, death)	
 Model-adjusted GMTs by vaccination group and visit Model-adjusted GMT ratios by visit Unadjusted GMTs/GMFRs from baseline by vaccination group and visit Seroresponse rate by vaccination group and post-baseline visit 	4.2.3
Exploratory	hMPV B nAb titers through Day 181				

Statistical category	Endpoint	Population	Intercurrent event strategy	Population level summary (analysis)	Details in section
				
• Difference in seroresponse rate by post-baseline visit	

4.2.1 Primary Immunogenicity Endpoint – RSV A Neutralizing Antibody Response at Day 29

The primary immunogenicity objective of the study is to characterize the nAb responses to RSV A in serum following vaccination with IVX-A12 or AREXVY.

4.2.1.1 Definition

The primary endpoint is the nAb concentration for RSV A at Day 29. The primary analyses will be conducted on data reported from samples analyzed by the GFP RSV A neutralization assay conducted at [REDACTED]. Planned supplementary analyses will be performed on results reported by other exploratory assays, as discussed below in Section 4.2.1.7. Evaluable participants will be those in the IAS with non-missing concentration value at both baseline and Day 29.

4.2.1.2 Derivations

Geometric mean concentration (GMC), geometric mean fold rise (GMFR) and their corresponding 95% CIs will be calculated, as defined in Section 3.4.1. A log base 2 transformation will be used for nAb response. Additionally, the seroresponse rate and corresponding 95% CI will be reported. Concentration values below LLoQ and above ULoQ will be imputed according to Section 3.4.

4.2.1.3 Handling of Intercurrent Events

Results from samples collected after the date of an intercurrent event will be excluded from the analysis.

Intercurrent events for immunogenicity analyses include:

- Occurrence of a protocol deviation that can interfere with an immune response
- Infection with RSV/hMPV
- Early withdrawal from the study
- Death

An infection with RSV/hMPV will be identified using data collected in the AE eCRF. The list of PTs (MedDRA 27.0) used to select AEs pertaining to these infections are included in Appendix A. Partial or missing dates of an infection with RSV/hMPV will be imputed as described in the Appendix B.

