3.4 General Considerations

Data will be provided in data listings sorted by vaccination group and participant number. Tabular summaries will be presented by vaccination group and overall. Vaccination group will be defined as the actual vaccination received by a randomized participant.

Categorical variables will be summarized using frequency and percentages, where the denominator for calculation is the underlying analysis set population, unless otherwise stated. Continuous variables will be summarized with descriptive statistics of number of available observations, mean, standard deviation, median, minimum, maximum, and quartiles where appropriate.

All point estimates will be presented with a two-sided 95% CI, unless otherwise stated. For subgroup analyses, CIs will be presented for subgroup categories which have at least 5 evaluable participants per vaccination group.

The RSV nAb responses are measured as concentrations in IU/mL and therefore the geometric mean responses will be referred to as GMCs while the hMPV nAb responses are measured as titers (1/dilution) and the geometric mean responses will be referred to as GMTs. The GMCs and GMTs are referred to generally as geometric mean responses.

Immunogenicity summaries involving the Day 29 endpoint will include participants in the immunogenicity analysis set with a non-missing baseline and a non-missing result at Day 29.

For immunogenicity summaries involving data through Day 181, evaluable participants will be those in the immunogenicity analysis set with non-missing baseline and at least one non-missing post-baseline (Day 29 or 181) result.

Immunogenicity results below the LLoQ will be imputed to half of the LLoQ and results above the ULoQ will be imputed to the ULoQ prior to computing geometric mean responses. Responses will be imputed before any model-adjustment is performed.

The data analyses will be conducted using the SAS® System version 9.4 or above (SAS Institute Inc., Cary, NC). All SAS® programs used to generate analytical results will be developed and validated according to AstraZeneca programming standards and validation procedures.

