4.6.2 Adverse Events

4.6.2.1 Definitions and Derivations

Adverse events experienced by participants will be collected throughout the study as listed below:

- Immediate unsolicited AEs within 30 minutes of dosing
- Solicited injection site and systemic ARs for 7 days post-vaccination (Day 1 to Day 8)
- Unsolicited AEs for 28 days post-vaccination (Day 1 to Day 29)
- SAEs from date of ICF through 6 months post-vaccination (Day 1 to Day 181)
- MAAEs, AESIs, and deaths over the entire study period (Day 1 to Day 181)

Serious adverse events collected prior to vaccination from ICF will be included in the listings only.

Intensity of AEs is determined by the investigator as mild, moderate, or severe. If there are AEs with missing intensity, the category “Missing” will be summarized separately from the non-missing categories. The relationship of AE to study vaccination will be assessed by the investigator and recorded in the AE eCRF as “Yes” or “No” to the question “Is this event related to study medication?” If there are AEs with missing relationship, the category “Missing” will be summarized separately from the non-missing categories. Partial or missing dates for AEs, SAEs, AESIs, and MAAEs will be imputed as described in Appendix B. Duration of AEs will not be calculated using imputed dates and will instead be set to missing in the listings.

Solicited ARs that are present on the last eDiary completion date (Day 8) may not have resolved on Day 8. The solicited ARs which have not resolved at Day 8 will be marked as a continuing event and documented as an unsolicited AE in the AE eCRF in order to collect the stop date of the adverse reaction. However, the continuing event will not be summarized as an unsolicited AE to avoid duplication. The start date for the continuing event will be the first day the solicited AR was first recorded in the eDiary; the stop date will be recorded in the AE eCRF. The duration of solicited ARs will be calculated as the last day of the adverse reaction – the first day of the adverse reaction + 1. Participants with a missing stop date for a solicited AR will not be included in the calculation of duration and will instead be summarized as missing.

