Appendix B Missing and Partial Dates for Adverse Events and Concomitant Medications

If an AE onset date is completely missing, then the AE will be assumed to be post-vaccination and will be included in all applicable summaries, unless the stop date indicates otherwise. If the AE onset date is partially missing, AE dates will be handled using the following imputation rules:

The missing start day will be set to:

- First day of the month of occurrence if the start YYYY-MM is after the YYYY-MM of study vaccination.
- The day of study vaccination, if the start YYYY-MM is the same as the YYYY-MM of study vaccination
- The date of informed consent, if the YYYY-MM is before the YYYY-MM of the study vaccination.

If the start date is missing both the day and month, the start date will be set to:

- The date of the study vaccination, if the start year is the same as the year of study vaccination.
- January 1 of the year of occurrence.

The missing end day will be set to:

- The last day of the month of the occurrence, if the YYYY-MM is after the YYYY-MM of the study vaccination.
- The day of data cutoff date, early study withdrawal date, death date or end of study date if the earliest of these occurred in the same YYYY-MM as the partial end date.

If the end date is missing both the day and month, the end date will be set to:

- The data cutoff date, early study withdrawal date, death date or end of study date if the earliest of these occurred in the same year as the AE onset
- December 31 of the year of occurrence

If the start date is null, the date will be set to:

- The date of study vaccination
- Date of informed consent if the end date is on or prior to the date of vaccination.

If the end date is null and the AE outcome indicates that the event is recovered, the end date will be set to:

- The date of study vaccination, if the start date is prior to the date of study vaccination.
- The earliest of the data cutoff date, early study withdrawal date, death date or end of study date.

If the end date is null and the AE outcome indicates that the event is not recovered, the end date will not be imputed.

The same method will be used for missing and partial start and end dates for concomitant medications.

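### Do the Appendix B date defaults wrongly delete Day 29 results when an RSV/hMPV infection date is incomplete?

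*SAP*

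**What the plan says.** SAP 4.2.1.3 lists RSV/hMPV infection as an intercurrent event for every immunogenicity analysis, identifies it from the AE eCRF through the Appendix A preferred terms, and states: "Results from samples collected after the date of an intercurrent event will be excluded from the analysis". For incomplete infection dates it adds: "Partial or missing dates of an infection with RSV/hMPV will be imputed as described in the Appendix B".

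The onset rules in Appendix B that matter here are:

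- Day missing, month later than the vaccination month: "First day of the month of occurrence if the start YYYY-MM is after the YYYY-MM of study vaccination". If the month is the vaccination month, the vaccination day is used.
- Day and month missing: "The date of the study vaccination, if the start year is the same as the year of study vaccination"; otherwise 1 January of the year of occurrence.
- Onset wholly missing: "If the start date is null, the date will be set to" the vaccination date, or the consent date if the event ended on or before vaccination.

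For the primary endpoint, SAP 4.2.1.1 says: "Evaluable participants will be those in the IAS with non-missing concentration value at both baseline and Day 29". For analyses through Day 181, SAP 3.4 asks for participants "with non-missing baseline and at least one non-missing post-baseline (Day 29 or 181) result". Deleted values are not imputed (4.2.1.4) and no sensitivity analysis is planned (4.2.1.6). SAP 4.2.3.1 carries the same intercurrent-event handling to the exploratory endpoints.

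**The concern.** Placing an undated adverse event early is cautious in a safety table, because the event is then counted. In the immunogenicity analysis the same early date removes data. Nothing in the SAP compares the imputed date with the sample date or with when the event was reported, so a Day 29 result that truly preceded the infection can be dropped.

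If the infection is on file at the primary data cut, the participant leaves the Day 29 ANCOVA. If it is recorded later, the loss falls on the final MMRM. There the true infection already excludes Day 181, so losing Day 29 as well leaves no post-baseline value. An hMPV infection can remove an RSV A result in this way, because either virus triggers the rule for every endpoint.

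The SAP also seems to recognise that imputed dates are unreliable. Section 4.6.2.1 says: "Duration of AEs will not be calculated using imputed dates and will instead be set to missing in the listings". It sets no such limit where those dates remove endpoint values.

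**Working it through.** **1. Does the chain work as feared?** Take vaccination on 15 May 2024, the Day 29 sample on 12 June and true onset on 24 June. Day missing gives 1 June. Day and month missing gives 15 May. Wholly missing gives 15 May. All three precede 12 June, so the result is deleted. The baseline is safe, because a sample on the vaccination day is not after an event dated to that day.

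**2. How often would a default date do this?** I took every vaccination date in 2024, a sample 28 days later, and a true onset on each of the following 152 days (Day 30 to Day 181). A deletion is counted when the sample date is later than the imputed date.

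| Onset date recorded | Days of 152 that delete Day 29 | Share |
|---|---|---|
| Month and year | mean 13.8 (range 0-29) | 9.1% |
| Year only | mean 119.8 | 79% |
| Nothing | 152 | 100% |

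The year-only share depends on season: 152/152 for April-June vaccination and 48/152 = 32% for September-November. The imputed date is never later than the true one, so every error runs towards deletion. Month-only dates cause an error only when onset falls in the same calendar month as the sample.

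**3. How many participants?** The documents give no rate of recorded infections or of incomplete dates, so this step rests on assumptions. Protocol 2.2.1 gives 3-7% a year for RSV infection in adults aged 65 and older. I borrow that for hMPV too and spread it evenly:

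- Infections after the Day 29 sample: 140 x 2 x 0.03 x 152/365 = 3.50, and with 0.07, 8.16.
- Assume half are recorded and 10% of those lack a full date: 3.50 x 0.5 x 0.10 = 0.175, and 8.16 x 0.5 x 0.10 = 0.408.
- All month-only: x 0.091 = 0.02 to 0.04 wrongful deletions in the whole trial.
- All year-only: x 0.79 = 0.14 to 0.32.
- All wholly missing: x 1 = 0.17 to 0.41.

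Varying the assumptions to 25-100% recorded and 5-30% incomplete gives 0.004-0.22, 0.03-1.9 and 0.04-2.4 respectively. The 2.4 needs every infection recorded, 30% of them with an incomplete date, and all of those dates blank.

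**4. What would one loss do?** The SD is redacted, so I recover it from SAP Table 1 (N = 140, ratio 1.0, 95% CI 0.63-1.58). The log half-width is ln(1.58/0.63)/2 = 0.460, and SD = 0.460 / (1.977 x sqrt(2/70)) = 1.376 on the natural-log scale. This returns 0.631-1.584, which rounds to the table's figures. With 69 against 70 participants the half-width goes from 0.4597 to 0.4614, and the interval becomes 0.630-1.586. If the lost value lies 1 SD from the mean, that group's GMC moves by a factor of exp(1.376/69) = 1.020, about 2%.

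**The case for a change.** The best case for a change is that the mechanism follows from the text as written, the error has one direction, no planned analysis would reveal it, and the remedy is a sentence or two. Protocol 6.4 already requires evaluability decisions to be documented before the codes are broken for the planned analyses, so a review of incomplete infection dates would fit an existing step. All of that stands as description.

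It does not carry the conclusion, for four reasons.

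- **Large counts need unlikely data.** The start date is a listed variable for every AE (Protocol 8.4). The higher figures need onset dates with no month, or no date at all.
- **The infection count is probably high.** After Day 29 only SAEs, MAAEs and AESIs are recorded (Protocol 8.4.1). The event must also code to an RSV- or hMPV-specific term, and the Schedule of Activities includes no respiratory swabs. The borrowed rate is for RSV infection of any kind and allows for no protection from either vaccine.
- **The primary analysis is largely spared.** A participant whose infection is recorded after the primary cut has already contributed to the Day 29 ANCOVA and is lost only from the final exploratory model.
- **The alternative has its own error.** Keeping a result whenever the order is unknown can retain a titer boosted by infection. Early dating is sometimes right: all unsolicited AEs are collected through Day 29, so an undated infection on file at the primary cut may well have come before the sample. Case-by-case decisions would replace a fixed rule, some of them after the primary results exist. The visit of first report, which such decisions would lean on, is not among the variables listed for a non-serious MAAE.

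The duration comparison adds little. In 4.6.2.1 imputed dates are barred only from duration, where the invented days would themselves be the reported figure. The same section uses Appendix B dates for AEs otherwise.

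**Conclusion.** No change is needed. SAP 4.2.1.3 with Appendix B can delete a valid Day 29 result, but the expected number is close to zero: 0.02-0.04 participants for month-only dates, and below 0.5 even if every incomplete date were blank. One loss changes the planned interval in the third decimal place and that group's GMC by about 2% for a value 1 SD out. The study is descriptive, so no formal conclusion hangs on it.

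How to treat a truly unknown order of infection and sample is a judgement, and a fixed, prespecified rule that errs towards excluding possibly boosted titers is a fair choice. If a case arises in which the recorded partial date or stop date settles the order, analysts can note it when evaluability is decided.

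The counts assume a 3-7% yearly rate for each virus spread evenly over the year, half of infections recorded and 10% of those with incomplete dates; the recording and missing-date rates are not in the documents. The conclusion would weaken only if blank or year-only infection dates proved common, towards the extreme of 2.4 participants.
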